3 OBJECTIVES AND ENDPOINTS

Aim 1: Test the efficacy of the intervention in slowing adiposity and weight gain trajectory and improving health behaviors (nutrition and physical activity) in 3-5-year-old Hispanic children from Time 1 (0 months [baseline]) to Time 2 (9 months [completion of the intervention]) and Time 1 to Time 3 (15 months [after 6 months with no contact from the study staff]).

Aim 2: Test the efficacy of the intervention in decreasing adiposity and weight and improving health behaviors and self-efficacy in overweight or obese Hispanic mothers from Time 1 to Time 2 and from Time 1 to Time 3.

Primary outcomes include slowing of child adiposity (waist circumference and triceps and subscapular skinfolds) and weight gain (BMI percentile) trajectory and a decrease in mother's adiposity and weight (BMI). We hypothesize that intervention group children will slow the trajectory of adiposity and weight gain and intervention group mothers will decrease adiposity and weight significantly more than the control group.

Secondary outcomes include child and mothers health behaviors (nutrition and physical activity) and mother's self-efficacy (nutrition and physical activity). We hypothesize that intervention group children and mothers will improve health behaviors and mothers will improve self-efficacy significantly more than the control group.

Aim 3: Identify the mediators through which the intervention influences the trajectory of adiposity and weight gain in children and decrease in adiposity and weight in mothers. We hypothesize that health behaviors and self-efficacy may mediate adiposity and weight loss in mothers and nutrition and physical activity behaviors in children may mediate a slower adiposity and weight gain trajectory.

Aim 4: Calculate the cost of implementing the intervention for public health departments and the costs for mothers participating, from Time 1 to Time 2 and compare these costs to the outcomes of the intervention (cost-effectiveness) and the potential economic benefits of these outcomes (cost-benefit analysis). We hypothesize that the intervention is primarily focused on knowledge and behaviors in an at-risk population and may be cost-effective in comparison with other approaches to managing overweight and obesity.

Exploratory Aim: Determine whether intervention group mothers in the overweight versus obese BMI category benefit equally from the intervention in adiposity, weight, health behaviors, and self-efficacy.

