9.2 SAMPLE SIZE DETERMINATION

A total of 250 mother-child dyads, or 125 dyads in each randomized group, are expected to complete the study. However, we will enroll 294 mother-child dyads ($n = 588$ participants) or 147 dyads per group, to take into account a 15% attrition rate. Our previous studies with Hispanic mothers with limited English proficiency and their children have had attrition rates ranging from 9% to 15% [23, 33]. Power calculations were performed with POWERLIB20 SAS/IML modules, which incorporate methods described in Muller [39]. These methods calculate power for a general linear multivariate model that includes repeated measures data structures, of which a two-group longitudinal design is a special case. Power was calculated on the use of a separate multivariate model for each outcome addressed in the aims, incorporating measurements at all available time points. Effect size estimates were based on the pilot data [23], where estimated within-subject correlation and standardized mean difference were .25 and .53, respectively, for mothers' BMI and .30 and .59, respectively, for children's BMI percentiles. For each outcome, power was computed for a test of the time by treatment interaction at a two-sided significance level of .05. For an analyzable sample of 125 mother-child dyads per group (total of 250 mother-child dyads), calculated statistical power exceeds 95% for both the test of children's BMI percentiles in Aim 1 and the test of mothers' BMI in Aim 2; if the within subject correlations and standardized mean differences are lower than observed in the pilot at .20 and .45, respectively, statistical power will nonetheless exceed 80%. A formal power analysis was not conducted for Aim 3 because the focus is on estimation (rather than testing) of direct and indirect mediation effects. Nonetheless, based on Shrout and Bolger [40], a sample size of 80 to 85 should provide power in the 70% to 85% range to detect medium effects of the intervention on the mediator (e.g., maternal self-efficacy), and the mediator on the outcomes (e.g.,

mother's BMI) with a two sided .05 significance level. Our 250 dyads should provide an adequate sample to quantify mediation of the relevant variables.

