Exploratory Aim: Analyses will be performed on weight status, adiposity, health behavior, and self-efficacy to explore whether the intervention effects for mothers are similar for those who are overweight (BMI 25-29.9kg/m²) and those who are obese (BMI ≥ 30 kg/m²). The mixed models described for Aims 1 and 2 will be implemented for each of the weight status, adiposity, health behavior, and self-efficacy variables, with the addition of four explanatory variables to each model: an indicator for the obese group, the interaction between this indicator and the indicator variable for group membership, the interaction between this indicator and time, and the three-way interaction among the group indicator, obese indicator, and time. The hypothesis test for the three-way interaction as well as the obesity indicator by group indicator interaction jointly equal to zero will indicate whether the intervention effects are homogeneous across BMI ranges. For each outcome, differences will be calculated to test the effects of the intervention versus control group at each follow-up point separately for each BMI range. Similar analyses will be performed with groupings of children in the 25th-84.9th percentile (normal weight), 85th-94.9th percentile (overweight) and $\geq 95^{\text{th}}$ percentile (obese).

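### With 250 dyads, a non-significant interaction test cannot show that overweight and obese mothers benefit equally, and the plan does not say whether that test or the separate within-range tests govern

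*Combined protocol and SAP*

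**What the plan says.** Section 3 words the Exploratory Aim as a question about equality: "Determine whether intervention group mothers in the overweight versus obese BMI category benefit equally from the intervention", for adiposity, weight, health behaviors and self-efficacy.

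Section 9.4.10 adds an obese indicator and its interactions with group and time to the Aim 1 and 2 mixed models. A test of the obese-by-group and three-way terms "jointly equal to zero will indicate whether the intervention effects are homogeneous across BMI ranges". The next sentence then plans within-range testing: "differences will be calculated to test the effects of the intervention versus control group at each follow-up point separately for each BMI range". This applies to every outcome, and the approach is to be repeated for three child BMI-percentile bands.

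Section 9.2 sizes the trial for the main comparison only: "power was computed for a test of the time by treatment interaction at a two-sided significance level of .05". For the Exploratory Aim the plan gives no margin for equal benefit, no power or precision, no multiplicity rule of its own, and no order of precedence between the joint test and the within-range tests.

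**The concern.** The only route the plan offers to an answer of equal benefit is a joint test that fails to reach significance. Failing to find a difference shows equality only if the test would probably have found a difference that matters. Contrasts between subgroups are much less precise than the main effect for which the trial was sized.

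The within-range tests then give a second set of p-values on the same question. Each uses only part of the sample, so they can disagree by chance when the true effects are identical, and the plan does not say how to read such a result. Someone deciding whether to offer the programme to overweight mothers, obese mothers or both would turn to this analysis.

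**Working it through.** **Inputs from Section 9.2.** Analyzable sample: "For an analyzable sample of 125 mother-child dyads per group", 250 in all. Pilot values: "estimated within-subject correlation and standardized mean difference were .25 and .53, respectively, for mothers' BMI". Children's pilot values are .30 and .59. Fallback values are correlation .20 and standardized mean difference (SMD) .45.

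**Assumptions, because the plan is silent.** The smaller BMI group holds 30-50% of mothers (no expected share is given, although Section 6.3 stratifies on it). Compound symmetry, unit SD, zero effect at Time 1, the same effect at Times 2 and 3, and alpha .05 for the exploratory tests.

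**1. The plan's own figures.** For the 2-df time-by-treatment test, λ = d²·(2/3) / [(1−ρ)·2/125].
- Mothers: .2809·.6667/(.75·.016) = 15.61, power about 95%.
- Children: .3481·.6667/(.70·.016) = 20.72, power 98.7%.
- Fallback: .2025·.6667/(.80·.016) = 10.55, power about 83%.

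These agree with the stated figures (above 95%, and above 80% for the fallback) to rounding. Also 250/.85 = 294.1, which matches the 294 enrolled.

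**2. The planned homogeneity test.** With three categorical time points it has 1 + 2 = 3 df. For a gap g between the two BMI-group effects at both follow-ups, λ = 2g² / [(1−ρ)(1+2ρ)k], where k = 4/n₁ + 4/n₂. At 125:125, k = .064. At 75:175, k = .0762.

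Take the simple average of the two effects as the SMD d. A twofold difference is then 4d/3 v 2d/3, a gap of 2d/3 (fallback: .60 v .30). A threefold difference is 3d/2 v d/2, a gap of d (fallback: .675 v .225). Worked example (fallback, threefold, equal split): λ = 2·.2025/(.80·1.40·.064) = 5.65, power 48%.

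| Inputs | Difference | Gap (SD) | Power, 30:70 to 50:50 |
|---|---|---|---|
| Fallback | twofold | .30 | 20-23% |
| Fallback | threefold | .45 | 41-49% |
| Pilot | twofold | .353 | 26-31% |
| Pilot | threefold | .53 | 55-63% |

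The test depends only on the gap, so the threefold rows also cover a full planned effect in one group and none in the other. That is missed in 37-59% of trials.

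**3. Precision of the between-group difference.**
- On change from Time 1, the 95% half-width is 1.96·√[k·2(1−ρ)]. At fallback and equal split this is 1.96·√(.064·1.6) = .63 SD. The range over splits and inputs is .61-.68 SD.
- On the group difference at a single time it is 1.96·√k, or .50-.54 SD.

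**4. Separate tests with identical true effects.** At an equal split, each range has 125 mothers.
- Fallback, change from Time 1: SE = √[(4/125)·1.6] = .226, z = .45/.226 = 1.99, power 51%. Exactly one range is significant with probability 2·.51·.49 = 50%.
- Pilot: SE = √[(4/125)·1.5] = .219, z = 2.42, power 68%, giving 2·.677·.323 = 44%.
- At 30:70 these become 55% and 52%, so the range is 44-55%.
- On the per-time difference, SE = √(4/125) = .179. Power is 71% (fallback) or 84% (pilot), and exactly one is significant in 41% or 27%. Over the splits the range is 27-50%.

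**5. Both procedures together.** A simulation of 200,000 trials per setting, with identical effects and tests on change from Time 1, gave exactly one range significant with a non-significant joint test in 40-51% of trials at a given follow-up. Exactly one range significant with a significant joint test occurred in about 3-4%.

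**The case against.** The analysis is labelled exploratory and carries no stated hypothesis. It uses a formal interaction test, and randomization is stratified by maternal BMI. Saying that an interaction test indicates whether effects are homogeneous is common wording and need not mean that a null result proves equality. The Aim 1 and 2 models are already to be summarized by least-squares means and mean differences with 95% intervals, so some estimation is arguably planned. A large gap would be seen: one of twice the SMD is detected in about 97% of trials or more.

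Most of this stands and limits the point. It does not supply an interval for the difference between the BMI-group effects, a caution about a null result, or a rule for conflicting results. A gap of twice the SMD means one group gaining .90 to 1.06 SD more than the other, so detecting it says little about differences of the planned size.

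A reader might infer more than the documents support:
- That the trial will report benefit in one BMI group only. No sentence says so. The 44-55% figure applies only if the within-range p-values are read on their own; if the joint test must also be significant, the error falls to about 3-4%.
- That power is as low as 15% (twofold) or 29% (threefold) at the fallback inputs and equal split. Those figures belong to the 2-df three-way terms alone, which is not the planned test.

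**Conclusion.** The point holds as a limit on what the Exploratory Aim can conclude. As worded, the plan lets a non-significant 3-df test stand for equal benefit, when that test misses a twofold difference in 69-80% of trials and a threefold one in 37-59%, across pilot and fallback inputs. The interval for the difference would extend about .5 to .7 SD either way, similar to or wider than the planned effects of .45 and .53. The plan also leaves open which result governs when the joint and within-range tests disagree.

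The documents do not support saying that the trial will usually reach a false conclusion of equality, since that depends on the true gap and on how the result is written up. The figures rest on the assumptions listed in the working, and the discordance rate also depends on whether the within-range test is read as change from Time 1 or as the difference at each time. The child bands were not computed, but with three bands at least one holds no more than a third of the children. No primary or secondary conclusion is affected.

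**What to change.** In Section 9.4.10, Exploratory Aim:
- Report, at Time 2 and at Time 3, the difference between BMI groups in the intervention effect on change from Time 1, with 95% confidence intervals.
- State that a non-significant joint test is not evidence of equal benefit.
- Present within-range effects as estimates with 95% confidence intervals, and rest any claim of a differential effect on the interaction contrast only.
- Apply the same rules to the three child bands.

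In Sections 3 and 9.1, reword the aim as estimating how the effect differs between overweight and obese mothers.

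The cost is wording only. The models already contain the terms needed, and no extra data, visits or participants are required.

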10 SUPPORTING DOCUMENTATION AND OPERATIONAL CONSIDERATIONS

10.1 REGULATORY, ETHICAL, AND STUDY OVERSIGHT CONSIDERATIONS

- 10.1.1.1 INFORMED CONSENT PROCESS
- 10.1.1.2 CONSENT/ASSENT AND OTHER INFORMATIONAL DOCUMENTS PROVIDED TO PARTICIPANTS
- 10.1.1.3 CONSENT PROCEDURES AND DOCUMENTATION

See human subjects section above for details of consent.

10.1.2 STUDY DISCONTINUATION AND CLOSURE

At the completion of five years or 60 months the study will be closed unless a no cost extension is needed.

10.1.3 CONFIDENTIALITY AND PRIVACY

See Human Subjects above.

Participant confidentiality and privacy is strictly held in trust by the participating investigators, their staff, the safety and oversight monitor(s), and the sponsor(s) and funding agency. This confidentiality is extended to the data being collected as part of this study. Data that could be used to identify a specific study participant will be held in strict confidence within the research team. No personally-identifiable information from the study will be released to any unauthorized third party without prior written approval of the sponsor/funding agency.

All research activities will be conducted in as private a setting as possible.

The study monitor, other authorized representatives of the sponsor or funding agency, representatives of the Institutional Review Board (IRB), regulatory agencies or representatives from companies or organizations supplying the product, may inspect all documents and records required to be maintained by the investigator for the participants in this study.

The study participant's contact information will be securely stored at the site for internal use during the study. At the end of the study, all records will continue to be kept in a secure location for as long a period as dictated by the reviewing IRB, Institutional policies, or sponsor/funding agency requirements.

Study participant research data, which is for purposes of statistical analysis and scientific reporting, will be transmitted to and stored on REDCap. This will not include the participant's contact or identifying information. Rather, individual participants and their research data will be identified by a unique study identification number. The study data entry and study management systems used by research staff will be secured and password protected. At the end of the study, all study databases will be de-identified and archived at the University of North Carolina at Chapel Hill School of Nursing.

Measures Taken to Ensure Confidentiality of Data Shared per the NIH Data Sharing Policies

It is NIH policy that the results and accomplishments of the activities that it funds should be made available to the public (see <https://grants.nih.gov/policy/sharing.htm>). The PI will ensure all mechanisms used to share data will include proper plans and safeguards for the protection of privacy, confidentiality, and security for data dissemination and reuse (e.g., all data will be thoroughly de-identified and will not be traceable to a specific study participant). Plans for archiving and long-term preservation of the data will be implemented, as appropriate.

Certificate of Confidentiality

To further protect the privacy of study participants, the Secretary, Health and Human Services (HHS), has issued a Certificate of Confidentiality (CoC) to all researchers engaged in biomedical, behavioral, clinical or other human subjects research funded wholly or in part by the federal government. Recipients of NIH funding for human subjects research are required to protect identifiable research information from forced disclosure per the terms of the NIH Policy (see <https://humansubjects.nih.gov/coc/index>). As set forth in 45 CFR Part

75.303(a) and NIHGPS Chapter 8.3, recipients conducting NIH-supported research covered by this Policy are required to establish and maintain effective internal controls (e.g., policies and procedures) that provide reasonable assurance that the award is managed in compliance with Federal statutes, regulations, and the terms and conditions of award. It is the NIH policy that investigators and others who have access to research records will not disclose identifying information except when the participant consents or in certain instances when federal, state, or local law or regulation requires disclosure. NIH expects investigators to inform research participants of the protections and the limits to protections provided by a Certificate issued by this Policy.

10.1.4 FUTURE USE OF STORED SPECIMENS AND DATA

Data collected for this study will be analyzed and stored at the University of North Carolina School of Nursing. After the study is completed, the de-identified, archived data will be transmitted to and stored at the University of North Carolina School of Nursing, for use by other researchers including those outside of the study.

10.1.6 SAFETY OVERSIGHT

Safety oversight will be under the direction of a Data and Safety Monitoring Plan (DSMP) composed of individuals with the appropriate expertise. See the DSMP for details.

10.1.7 CLINICAL MONITORING

N/A

10.1.8 QUALITY ASSURANCE AND QUALITY CONTROL

Procedures will be followed according to standard protocols for height, weight, calculation of BMI and BMI percentile and collection of anthropometric measurements and questionnaire and accelerometry and 24 hour food recall data.

Quality control (QC) procedures will be implemented as follows:

Informed consent --- Study staff will review both the documentation of the consenting process as well as a percentage of the completed consent documents. This review will evaluate compliance with GCP, accuracy, and completeness. Feedback will be provided to the study team to ensure proper consenting procedures are followed.

Source documents and the electronic data --- Data will be initially captured on source documents and will ultimately be entered into the study database. To ensure accuracy site staff will compare a representative sample of source data against the database, targeting key data points in that review.

Intervention Fidelity — Consistent delivery of the study interventions will be monitored throughout the intervention phase of the study. Procedures for ensuring fidelity of intervention delivery are described above.

Protocol Deviations – The study team will review protocol deviations on an ongoing basis and will implement corrective actions when the quantity or nature of deviations are deemed to be at a level of concern.

Should independent monitoring become necessary, the PI will provide direct access to all trial related sites, source data/documents, and reports for the purpose of monitoring and auditing by the sponsor/funding agency, and inspection by local and regulatory authorities.

10.1.9 DATA HANDLING AND RECORD KEEPING

10.1.9.1 DATA COLLECTION AND MANAGEMENT RESPONSIBILITIES

Data collection will be the responsibility of the Principal Investigator at the site under the supervision of the Project Manager. The investigator will be responsible for ensuring the accuracy, completeness, legibility, and timeliness of the data reported.

All source documents will be completed in a neat, legible manner to ensure accurate interpretation of data.

Hardcopies of the study visit worksheets will be provided for use as source document worksheets for recording data for each participant consented/enrolled in the study. Data recorded in the electronic case report form (eCRF) derived from source documents will be consistent with the data recorded on the source documents.

Clinical data will be entered into REDCap, a 21 CFR Part 11-compliant data capture system provided by the University of North Carolina at Chapel Hill. The data system includes password protection and internal quality checks, such as automatic range checks, to identify data that appear inconsistent, incomplete, or inaccurate. Clinical data will be entered directly from the source documents.

10.1.9.2 STUDY RECORDS RETENTION

Study documents will be retained for a minimum of 5 years.

10.1.10 PROTOCOL DEVIATIONS

This protocol defines a protocol deviation as any noncompliance with the clinical trial protocol, International Council on Harmonisation. The noncompliance may be either on the part of the participant, the investigator, or the study site staff. As a result of deviations, corrective actions will be developed by the site and implemented promptly.

10.1.11 PUBLICATION AND DATA SHARING POLICY

This study will be conducted in accordance with the following publication and data sharing policies and regulations:

National Institutes of Health (NIH) Public Access Policy, which ensures that the public has access to the published results of NIH funded research. It requires scientists to submit final peer-reviewed journal manuscripts that arise from NIH funds to the digital archive PubMed Central upon acceptance for publication.

This study will comply with the NIH Data Sharing Policy and Policy on the Dissemination of NIH-Funded Clinical Trial Information and the Clinical Trials Registration and Results Information Submission rule. As such, this trial will be registered at ClinicalTrials.gov, and results information from this trial will be submitted to ClinicalTrials.gov. In addition, every attempt will be made to publish results in peer-reviewed journals. Data from this study may be requested from other researchers 5 years after the completion of the primary endpoint by contacting the Principal Investigator.

